6.2.4 Evaluating Adverse Events

AE Grade

An investigator who is a qualified physician will evaluate all adverse events according to the NCI Common Terminology for Adverse Events (CTCAE), version 4.0. A copy of the CTCAE Version 4.0 can be downloaded from the CTEP website at: https://ctep.cancer.gov/protocoldevelopment/electronic_applications/ctc.htm

Any adverse event which changes CTCAE grade over the course of a given episode will have each change of grade recorded on the adverse event case report forms/worksheets.

When specific adverse events are not listed in the CTCAE they will be graded by the investigator according to the following grades and definitions, consistent with the CTCAE Version 4.0.

- Grade 1: Mild; asymptomatic or mild symptoms; clinical or diagnostic observations only; intervention not indicated.
- Grade 2: Moderate; minimal, local or noninvasive intervention indicated; limiting age-appropriate instrumental activities of daily living (ADL). Instrumental ADL refer to

preparing meals, shopping for groceries or clothes, using the telephone, managing money, etc.

- Grade 3: Severe or medically significant but not immediately life-threatening; hospitalization or prolongation of hospitalization indicated; disabling; limiting self care ADL. Self care ADL refer to bathing, dressing and undressing, feeding self, using the toilet, taking medications, and not bedridden
- Grade 4: Life-threatening consequences; urgent intervention indicated.
- Grade 5: Death related to AE.

Duration

The investigator will record the start and stop dates of the adverse event. If less than 1 day, this will be indicated in the appropriate length of time in units.

Action Taken

Did the adverse event cause the trial treatment to be discontinued?

Relationship

All adverse events regardless of CTCAE grade must also be evaluated for relationship (in regards to trial treatment/ trial interventions).

The determination of the likelihood that trial treatment caused the adverse event will be provided by an investigator who is a qualified physician. The investigator's signed/dated initials on the source document or worksheet that supports the causality noted on the AE form, ensures that a medically qualified assessment of causality was done. This initialed document must be retained for the required regulatory time frame.

The criteria below are intended as reference guidelines to assist the investigator in assessing the likelihood of a relationship between the trial treatment and the adverse event based upon the available information.

The following components are to be used to assess the relationship between trial treatment and the AE; the greater the correlation with the components and their respective elements (in number and/or intensity), the more likely the trial treatment caused the adverse event (AE):

Exposure: Is there evidence that the patient was actually exposed to trial treatment such as: reliable history, acceptable compliance assessment (pill count, diary, etc.), expected pharmacologic effect, or measurement of drug/metabolite in bodily specimen?

Time Course: Did the AE follow in a reasonable temporal sequence from administration of trial treatment? Is the time of onset of the AE compatible with a drug-induced effect?

Likely Cause: Is the AE not reasonably explained by another etiology such as underlying disease, other drug(s)/vaccine(s), or other host or environmental factors?

Dechallenge: Was trial treatment discontinued or dose/exposure/frequency reduced?

If yes, did the AE resolve or improve? **If yes,** this is a positive dechallenge.

If no, this is a negative dechallenge.

Note: This criterion is not applicable if: (1) the AE resulted in death or permanent disability; (2) the AE resolved/improved despite continuation of the trial treatment; or (3) the trial is a single-dose drug trial); or (4) trial treatment is/are only used one time.

Rechallenge: Was the patient re-exposed to trial treatment in this trial?

If yes, did the AE recur or worsen?

If yes, this is a positive rechallenge.

If no, this is a negative rechallenge.

Note: If a rechallenge is planned for an adverse event which was serious and which may have been caused by either of the trial treatments, or if re-exposure to trial treatment poses additional potential significant risk to the patient, then the rechallenge must be approved in advance by the Sponsor as per dose modification guidelines in the protocol.

Consistency with Trial Treatment Profile: **Is the clinical/pathological presentation of the AE consistent with previous knowledge regarding trial treatment or drug class pharmacology or toxicology?**

| Relationship | Attribution | Description |
|--|-------------|---|
| Unrelated to the trial treatment/intervention | Unrelated | The AE is clearly NOT related to the trial treatment/intervention |
| | Unlikely | The AE is doubtfully related to the trial treatment/intervention |
| Related to the trial treatment/intervention | Possible | The AE may be related to trial treatment/intervention |
| | Definite | The AE is clearly related to trial treatment/intervention |

6.2.5 Investigator Responsibility for Reporting Adverse Events

All Adverse Events will be reported to regulatory authorities, IRB/IECs and investigators in accordance with all applicable global laws and regulations.

7.0 LABELING, PACKAGING, STORAGE AND RETURN OF CLINICAL SUPPLIES

The investigator shall take responsibility for and shall take all steps to maintain appropriate records and ensure appropriate supply, storage, handling, distribution and usage of investigational product in accordance with the protocol and any applicable laws and regulations.

For the purposes of this trial the investigational products refer to both paricalcitol (or placebo) and pembrolizumab.

Paricalcitol will not be provided directly to the site as part of this trial but will be obtained directly from the treating investigator's designated pharmacy supply. Therefore the labeling, storage and, handling, of paricalcitol will follow the dispensing pharmacy's own standard operating procedures.

Pembrolizumab will be provided by Merck in temperature-controlled shipments directly to the site Pharmacy as summarized in Table 10 below. The details for the labeling, storage, handling, and disposal of pembrolizumab provided for use in this trial are therefore detailed below.

Table 10. Pembrolizumab Descriptions

| Product Name & Potency | Dosage Form |
|-----------------------------------|----------------------------------|
| Pembrolizumab 100mg/4 mL | Solution for Injection |
| Pembrolizumab 50 mg | Lyophilized Powder for Injection |

7.1 Packaging and Labeling Information

Pembrolizumab will be provided by Merck and will not be distinguished from the commercial product. Therefore, Investigator sites will be required to confirm prior to site initiation and pembrolizumab shipment, their specific plans for maintaining the trial supplied pembrolizumab separate from the pharmacy supply and how this will be distinguished for other pharmacy staff on site.

7.2 Storage and Handling Requirements

Pembrolizumab must be stored in a secure, limited-access location under the storage conditions specified on the label.

The investigator or authorized person at the trial site must maintain records of receipt and ongoing inventory of clinical trial supply of pembrolizumab at the site including the dispensing and administration of the pembrolizumab vials used for each patient.

Clinical trial supplies of pembrolizumab may not be used for any purpose other than that stated in the protocol.

7.3 Returns and Reconciliation

Upon completion or termination of the trial, all unused and/or partially used investigational product will be destroyed at the site per institutional policy. It is the Investigator's responsibility to arrange for disposal of all empty containers, provided that procedures for proper disposal have been established according to applicable federal, state, local and institutional guidelines and procedures, and provided that appropriate records of disposal are kept.

8.0 STATISTICAL CONSIDERATIONS

8.1 Trial Design

This is a randomized, double blind, placebo-controlled clinical trial. Eligible patients will be randomized in a 1:1 ratio to one of two treatment arms: pembrolizumab + paricalcitol or pembrolizumab + placebo.

Trial treatment will be administered every three weeks per the schedule as described in 4.2. The percent of patients with disease progression at six months will be the primary endpoint. Secondary endpoints will include: incidence of toxicities, overall survival, mutational landscape, transcriptional programs and cellular (immunity) VDR targets in the immune microenvironment.

8.2 Sample Size Considerations

The primary endpoint is the percentage of patients progressing at 6 months. Based on a contemporary control of no maintenance after best response to prior chemotherapy⁸, the control arm with pembrolizumab alone is expected to have only 8% of patients with no progression at 6 months. To be of clinical interest, at least 58% of patients must be progression-free at 6 months on the pembrolizumab plus paricalcitol arm. A sample size of 12 patients per arm will provide 90% statistical power to detect this difference assuming a one-sided alpha level of 0.05. A one-sided test was selected as we are only interested in the combination if it decreases the percentage of patients progressing at 6 months. This sample size estimate was obtained using binomial enumeration of all possible outcomes to compare two independent binomial proportions (Pearson's chi-squared test) using PASS 15.¹⁸ A statistical concern is that the Pearson chi-squared test does not guarantee the alpha level. We confirmed that we have adequate statistical power using the Miettinen & Nurminen¹⁹ exact likelihood score method (89% power) using Pass 15.

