20. Has received a live vaccine within 30 days of planned start of trial therapy.

Note: Seasonal influenza vaccines for injection are generally inactivated flu vaccines and are allowed; however intranasal influenza vaccines (e.g., Flu-Mist®) are live attenuated vaccines, and are not allowed.

Statistical Methods: The primary endpoint for this clinical trial is the percent of patients with radiographic disease progression according to RECIST 1.1 at 6 months. Without maintenance therapy, 92% of patients are expected to progress by 6 months. Therefore, we assume 1/12 (0.083) pembrolizumab + placebo arm show no progression versus 7/12 pembrolizumab + paricalcitol. This gives 90% statistical power with one side alpha = (0.05).

Statistical analysis will compare the proportion progression free at 6 months using a one-sided test comparing binomial proportions (equivalent to a Pearson's chi-square test). The incidence of toxicities will be tabulated. Overall survival will be estimated for each arm using a Kaplan-Meier estimate. Statistical comparison of overall survival will be performed using a log-rank test with estimation of the hazards ratio using a Cox proportional hazards model.

TABLE OF CONTENTS

| | |
|---|----|
| 1.0 BACKGROUND AND RATIONALE | 24 |
| 1.1 Overview | 24 |
| 1.2 A major developing problem in the care of patients with advanced pancreatic cancer | 24 |
| 1.3 Rationale - The reasoning behind a maintenance regimen | 25 |
| 1.4 Pembrolizumab (Keytruda®) | 26 |
| 1.5 Paricalcitol (Zemlar®) | 29 |
| 1.6 Trial Dose Rationale and Sequence | 30 |
| 1.6.1 Pembrolizumab Dose | 30 |
| 1.6.2 Paricalcitol Dose | 31 |
| 2.0 HYPOTHESIS..... | 32 |
| 3.0 OBJECTIVES | 32 |
| 3.1 Primary Objective | 32 |
| 3.2 Secondary Objectives..... | 32 |
| 3.3 Exploratory Objectives..... | 32 |
| 3.4 Primary Endpoints | 33 |
| 3.5 Secondary Endpoints | 33 |
| 3.6 Exploratory Endpoints | 33 |
| 4.0 METHODS..... | 33 |
| 4.1 Eligibility | 33 |
| 4.1.1 Inclusion Criteria | 34 |
| 4.1.2 Exclusion Criteria | 35 |
| 4.2 Trial Treatments | 37 |
| 4.2.1 Dose Selection/Modification | 37 |
| 4.2.2 Paricalcitol (Zemlar®) and Placebo | 38 |
| 4.2.3 Pembrolizumab (Keytruda®)..... | 38 |
| 4.2.4 Dose Modification (Escalation/Titration/Other) of Pembrolizumab (Keytruda®) in cases of Toxicity..... | 39 |
| 4.2.5 Dose Interruption of Paricalcitol in Cases of Toxicity | 44 |
| 4.2.6 Timing of Dose Administration..... | 44 |
| 4.2.7 Trial Blinding/Masking | 45 |

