8.3.4 Analysis of Primary Endpoint - Disease progression at 6 months

All patients that receive trial treatment will be included in the analysis to determine the percentage of patients progressing by RECIST 1.1 criteria at 6 months when maintained on a combination regimen of paricalcitol plus pembrolizumab versus pembrolizumab alone. The 6-month time-point will be defined as 6 months (180 days) from the initial treatment (cycle 1/day 1). Statistical analysis will compare the proportion progression free at 6 months using a one-sided test of binomial proportions (equivalent to a Pearson's chi-squared test). If the assumptions of the Pearson's chi-squared test are not met, we will analyze the data using Barnard's exact unconditional test of equality, as implemented in StatXact²⁰

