7 STATISTICAL METHODOLOGY

7.1 STATISTICAL PROCEDURES

Primary outcome: Progression-free survival

The proportion of patients in each arm who are progression-free at 6-months will be compared using a one-sided test of binomial proportions (equivalent to a Pearson's chi-squared test). If the assumptions of the Pearson's chi-squared test are not met, Barnard's exact unconditional test of equality will be used, as implemented in StatXact.

Patients unevaluable for progression at 6-months due to a non-progression related event will be excluded from analysis.

Statistical comparison of progression-free survival between the two treatment arms will be performed using a log-rank test, with estimation of the hazards ratio using a Cox proportional hazards model. A sensitivity analysis will include patients with an outcome of death due to another cause (other than progressive disease), which will be considered a competing event for progression. Analysis will be performed using the Fine and Gray (1999) approach.

Secondary outcome 1: Toxicity

All adverse events (AE) occurring on or after C1/D1 will be summarized by body systems and per grade according to NCI-CTCAE Version 4. Additionally, all serious adverse events (SAE) and events of clinical interest (ECI) will be listed separately and tabulated. ECIs for this trial include an overdose of pembrolizumab and an elevated AST or ALT lab value, as defined in section 6.2.3.2 of the protocol. All patients who receive any amount of trial treatment will be included in the analysis. The proportion of patients in each arm with toxicity will be compared using a chi-squared test or Barnard's exact unconditional test of equality as outlined above.

Secondary outcome 2: Overall survival

Overall survival will be calculated for each arm using a Kaplan-Meier estimate. Statistical comparison of overall survival between the two treatment arms will be performed using a log-rank test, with estimation of the hazards ratio using a Cox proportional hazards model. Patients with an outcome of death due to another cause (other than progressive disease) will be considered a competing event for death. Analysis will be performed using the Fine and Gray (1999) approach.

Exploratory outcome 1: RECIST 1.1 versus iRECIST

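### The stated 90% power at one-sided 5% alpha belongs to Pearson's test alone; the planned Pearson-or-Barnard switch has no stated trigger, and no expected-count trigger gives both properties

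*Protocol*

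**What the plan says.** Protocol 8.2 gives the design: progression-free at 6 months in 8% of the control arm and 58% of the combination arm, and "A sample size of 12 patients per arm will provide 90% statistical power to detect this difference assuming a one-sided alpha level of 0.05". The method stated there is enumeration of binomial outcomes for Pearson's test. The section then adds a caveat, "A statistical concern is that the Pearson chi-squared test does not guarantee the alpha level", and answers it with a second power figure, from the Miettinen and Nurminen "exact likelihood score method (89% power) using Pass 15".

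The analysis sections plan something else. Protocol 8.3.4: "If the assumptions of the Pearson's chi-squared test are not met, we will analyze the data using Barnard's exact unconditional test of equality". SAP 7.1: "If the assumptions of the Pearson's chi-squared test are not met, Barnard's exact unconditional test of equality will be used, as implemented in StatXact". Neither says which assumptions, what threshold, or whether expected or observed counts are meant. The synopsis gives the rates as 1/12 and 7/12, repeats the 90%, and names only the Pearson-type test, with no switch. No section gives power or size for Barnard's test or for the combined rule.

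SAP 7.1 also removes some patients from the comparison: "Patients unevaluable for progression at 6-months due to a non-progression related event will be excluded from analysis".

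**The concern.** A stated power and alpha should describe the procedure that decides the trial. Here they describe one branch of a two-branch rule, and the branch point is missing. At the design's own expected result, 1/12 versus 7/12, the smallest expected count is 4. Under the common convention that Pearson needs expected counts of at least 5 (an assumption; the documents do not state it), that result would go to Barnard. The 90% would then describe a test the trial usually does not use.

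Two things are at stake. The real power may be below the stated 90%, or the real maximum type I error above 5%, depending on an unwritten choice. And because the trigger is unwritten, it could be settled after the data are seen, in the few tables where it decides significance.

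**Working it through.** **Inputs.** 12 per arm, one-sided alpha 0.05, rates 0.08 and 0.58 (Protocol 8.2), or 1/12 and 7/12 (synopsis). Below, (a, b) is the number progression-free on control and on the combination. Power is shown at 1/12 versus 7/12, with 0.08 versus 0.58 in brackets.

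**Formulas.** All 13 × 13 outcomes are enumerated.

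- Power = Σ Bin(a; 12, pC) · Bin(b; 12, pE) over the tables that reject. Maximum size is the largest value of the same sum with pC = pE = p, over all p.
- Pearson: z = [(b − a)/12] / √[p̄(1 − p̄) · 2/12], with p̄ = (a + b)/24; reject if z > 1.645.
- Miettinen–Nurminen score with the asymptotic cut-off: reject if z · √(23/24) > 1.645.
- Barnard: p-value = the largest probability, over p, of a z at least as large as observed.
- Smallest expected count = the smaller of (a + b)/2 and (24 − a − b)/2.

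**The plan's own figures.** Pearson: 90.1% (90.3%), which matches 90%. Miettinen–Nurminen: 88.8% (89.1%), which matches 89%. Both are right for those tests. Their maximum sizes are 6.3% and 5.3%.

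**Where Pearson and Barnard disagree.** Four tables only; Pearson rejects and Barnard does not. For (2, 6): p̄ = 1/3, z = 0.3333/0.1925 = 1.732. For (3, 7): p̄ = 10/24, z = 0.3333/0.2013 = 1.656. The other two are mirror images.

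| Table | Smallest expected count | Pearson p | Barnard p | Probability at 1/12 vs 7/12 |
|---|---|---|---|---|
| 2/12 vs 6/12 | 4 | 0.042 | 0.053 | 3.66% |
| 3/12 vs 7/12 | 5 | 0.049 | 0.063 | 1.33% |
| 5/12 vs 9/12 | 5 | 0.049 | 0.063 | 0.02% |
| 6/12 vs 10/12 | 4 | 0.042 | 0.053 | 0.001% |

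The probabilities sum to 5.0%, which is the whole gap between Pearson (90.1%) and Barnard (85.1%).

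**Every expected-count trigger.** The disputed tables have smallest expected counts of 4 or 5, so only three procedures are possible.

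| Barnard used when the smallest expected count is | Power | Maximum size | Size above 5% at common rates |
|---|---|---|---|
| <1, <2, <3 or <4 | 90.1% (90.3%) | 6.3% | 0.18–0.82 |
| <5 | 86.4% (86.7%) | 5.4% | 0.38–0.62 |
| ≤5 | 85.1% (85.5%) | 4.7% | none |

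Observed-count triggers give the same three procedures; any observed count below 5, for example, gives the last row. Under the design alternative the <5 rule would send 78% (79%) of outcomes to Barnard.

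**Type I error at particular common rates.** At 8%: 2.5% for Pearson, for the <5 switch and for Barnard. At 22%, the progression-free complement of the 78% progressing on sunitinib in Protocol 1.3: 5.3%, 4.7% and 4.6%.

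**The case against.** The strongest reply is that nothing is miscalculated. The 90% is labelled in 8.2 as Pearson's and it reproduces. If alpha is read at the planned control rate of 8%, every version has type I error of about 2.5%, so triggers up to <4 do deliver 90% power with alpha well under 5%. The conventional reading of the assumptions is <5, and size then exceeds 5% only at common rates of 0.38 to 0.62, far from anything expected. The disputed tables are rare, and the expected result, 1/12 versus 7/12, has p = 0.005 under either test. Writing down a threshold would remove the ambiguity without dropping Pearson. Finally, 8.2 offers the 89% as a check on power and calls the method exact; that an asymptotic cut-off was used is inferred from the matching number.

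Much of this stands: the effect is small and the arithmetic is sound. Three points remain. Reading alpha as control over all common rates is the protocol's own concern in 8.2, and a power figure cannot answer it. The 8% comes from patients given no maintenance treatment, whereas this control arm receives pembrolizumab; Pearson's excess begins at a common rate of about 18%. And writing down the conventional <5 threshold would still leave power at 86.4% and maximum size at 5.4%, so the claim in 8.2 would still need changing.

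**Conclusion.** The concern holds. The planned primary procedure is not fully specified, and no expected-count trigger gives it both properties claimed in 8.2. Depending on the trigger, power is between 85% and 90% and maximum type I error between 4.7% and 6.3%; under the conventional <5 rule, power is about 3.5 points below the stated 90%. The 89% does not settle the alpha question, since the cut-off that reproduces it has a maximum size of 5.3%. This should be corrected, but it does not undermine the design. The conclusion assumes 12 evaluable patients per arm and alpha read as maximum size over the common rate.

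**What to change.** Before unblinding, name one exact unconditional test as the sole primary test in Protocol 8.2, 8.3.4, the synopsis and SAP 7.1. Delete the Pearson step and the switch, and state that test's own properties. Two candidates at 12 per arm:

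- Barnard, already in the plan: power 85.1% (85.5%), maximum size 4.7%.
- Boschloo: power 88.2% (88.4%), maximum size 4.95%.

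They disagree at 2/12 versus 6/12 (Barnard p = 0.053, Boschloo 0.0495), at 0/12 versus 3/12 (Barnard 0.047, Boschloo 0.063) and at the mirror images of these tables, so the choice must be fixed in advance.

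Possible wording for 8.2: *With 12 evaluable patients per arm, Barnard's exact unconditional test has 85% power (8% versus 58% progression-free) at one-sided alpha 0.05; its maximum size is 4.7%.*

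Remove the 89% as reassurance on alpha. Say that the power assumes 24 evaluable patients, because SAP 7.1 excludes some: at 11 per arm it is 81.7–82.1% (Barnard) or 84.5–84.7% (Boschloo).

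The cost is wording in four places and a lower stated power, 85% or 88% in place of 90%. No more patients are needed. Restoring 90% with Barnard would take 14 per arm (90.7–90.9%), which is not requested.

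### Section 8.2 offers an exact 89% power as its answer to the alpha concern, but 89% matches the large-sample score test, whose maximum error is 5.29%; an exact test on that statistic has 85%

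*Protocol*

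**What the plan says.** Protocol section 8.2 plans on a control arm "expected to have only 8% of patients with no progression at 6 months" and a target that "at least 58% of patients must be progression-free at 6 months on the pembrolizumab plus paricalcitol arm". The synopsis gives the same rates as fractions: "we assume 1/12 (0.083) pembrolizumab + placebo arm show no progression versus 7/12 pembrolizumab + paricalcitol". Section 8.2 then claims "90% statistical power to detect this difference assuming a one-sided alpha level of 0.05", obtained by binomial enumeration of Pearson's test at 12 per arm.

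It goes on: "A statistical concern is that the Pearson chi-squared test does not guarantee the alpha level". The reply, in the next sentence, is that power was confirmed to be adequate with the Miettinen-Nurminen "exact likelihood score method (89% power) using Pass 15". Section 8.2 gives no attained type I error for either test.

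For the analysis itself, section 8.3.4 specifies Pearson's test and says that if its assumptions are not met "we will analyze the data using Barnard's exact unconditional test of equality, as implemented in StatXact". SAP section 7.1 repeats this. Neither document gives a power for Barnard's test.

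**The concern.** The 89% follows directly on the admission that Pearson's test may exceed its level, and the method is called exact. The natural reading is that power stays at 89% once alpha is guaranteed. That holds only if 89% is the power of a test that guarantees alpha. If it comes from comparing the score statistic with a normal critical value, that test shares the weakness it was brought in to answer, and the reader still has no power figure for an analysis that holds 5%.

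The missing figure has practical use, because the planned fallback is an exact test and may well be needed. At 1/12 v 7/12 the expected table has 1 + 7 = 8 progression-free patients, so an expected count of 8/2 = 4 in each arm. The documents do not define when Pearson's assumptions fail. Under the common rule of expected counts of at least 5 (my assumption), the design scenario itself would lead to Barnard's test.

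**Working it through.** **Inputs.** 12 per arm and one-sided 0.05 (Protocol 8.2). Progression-free rates 1/12 v 7/12 (synopsis), or 8% v 58% (8.2). All 12 patients per arm are taken as evaluable, as 8.2 does.

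**Method.** Let a and b be the numbers progression-free on control and combination, each 0 to 12, giving 13 x 13 = 169 tables.

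- Pearson: z = (b - a)/12 divided by sqrt[p(1 - p)(2/12)], with p = (a + b)/24.
- Miettinen-Nurminen at zero difference: the same z multiplied by sqrt(23/24) = 0.979.
- Large-sample version: reject if the statistic is at least 1.645.
- Exact unconditional version: reject on the largest region ordered by the statistic whose null probability, maximised over the common rate, is at most 0.05.
- Power is the sum of Bin(a; 12, p0) x Bin(b; 12, p1) over the rejected tables. Size is the same sum with p0 = p1, maximised over the common rate.

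**Results.** The two stated figures come first.

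| Test | Power, 1/12 v 7/12 | Power, 8% v 58% | Maximum size |
|---|---|---|---|
| Pearson at 1.645 | 90.1% | 90.3% | 6.29% |
| Miettinen-Nurminen at 1.645 | 88.8% | 89.0% | 5.29% |
| Exact unconditional, Miettinen-Nurminen statistic | 85.1% | 85.5% | 4.68% |
| Exact unconditional, unpooled ordering | 85.1% | 85.5% | 4.68% |
| Barnard, CSM ordering | 85.3% | 85.7% | 4.78% |

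The stated 90% reproduces for Pearson and the stated 89% for the large-sample score test. The exact test on the same statistic falls about 4 points short of 89%. The exact test on the pooled z has the same rejection region, because the two statistics differ only by a constant factor.

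**Where the gap arises.** The large-sample and exact score regions differ in two tables, 2/12 v 6/12 and its mirror 6/12 v 10/12. For 2/12 v 6/12:

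- p = 8/24 = 1/3, and the standard error is sqrt[(1/3)(2/3)(2/12)] = 0.1925.
- z = 0.3333/0.1925 = 1.732, and the Miettinen-Nurminen value is 1.732 x 0.979 = 1.696. This exceeds 1.645, so the large-sample test rejects.
- Adding this tied pair to the exact region raises its maximum size from 4.68% to 5.29%, so the exact test must leave it out. Barnard's p-value for the table is 0.053.
- At the design rates its probability is 66(1/12)^2(11/12)^10 x 924(7/12)^6(5/12)^6 = 0.192 x 0.191 = 0.037. That accounts for the gap of 88.8 - 85.1 = 3.7 points.

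**Where the size exceeds 5%.** The large-sample score test is above 5% for common rates of about 18.5-35% and 65-81.5%, with its maximum near 27% and 73%. At 8% its size is about 2.5%.

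**The case against.** The strongest reply is that neither stated power is miscalculated. Both reproduce, and the sentence literally claims only adequate power, which 85% still supports. That stands. What does not survive is the use of the word exact to answer a concern about alpha.

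The source of the 89% is also not shown. Without the PASS output, assigning it to the large-sample test rests on matching a rounded figure. The match is close for the method named. The nearest size-controlling alternative computed, Boschloo's test, has 88.2% (88.4% at 8% v 58%), which rounds to 88%, and it is not the method named. This is still inference, so the output should be checked before the text is changed.

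Three stronger readings are tempting, and the documents support none of them:

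- A reader might infer that the 5.29% inflates this trial's error rate. The Miettinen-Nurminen test is not the planned analysis. The planned tests are Pearson's, with Barnard's as fallback, and the excess is at most 5.29 - 5 = 0.29 points and absent at the planned control rate.
- A reader might infer that the trial is underpowered. At the design effect, 85% remains usable power.
- A reader might infer that Barnard's test should give way to Boschloo's because the latter's 88% is nearer the stated figure. Both are valid exact tests. Boschloo's gains 2/12 v 6/12 and 6/12 v 10/12 but loses 0/12 v 3/12 and 9/12 v 12/12. Choosing a test to fit a planning figure is not a correction.

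**Conclusion.** The point holds as a correction to one stated power and its label. The 89% matches the large-sample Miettinen-Nurminen test, which does not guarantee 5%. With alpha held by an exact unconditional test on that statistic, or by Barnard's test under the orderings computed, power is about 85%. The chance of missing the target effect is then about 15% (100 - 85), against the 10-11% that the stated 90% and 89% imply.

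This rests on three things: all 12 patients per arm being evaluable; the 89% having been computed at the stated rates; and Barnard's test using one of the orderings tried, since the documents do not say which ordering is meant. The design stands, and the consequence is limited to what 8.2 tells the reader.

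**What to change.** Check the PASS output behind the 89%. If it confirms the match, restate Protocol section 8.2 to say that:

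- the 89% is the power of the large-sample Miettinen-Nurminen score test, with a maximum one-sided error of 5.3%;
- power is about 85% when alpha is held at 5% by the exact unconditional (Barnard) test named in 8.3.4 and SAP 7.1.

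If the output shows a different method, name it and give its attained maximum alpha. The about 85% for Barnard's test should be added either way.

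The cost is a few words in 8.2 and a slightly less favourable stated power. No test, analysis rule or patient number changes.
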